8.2.5. Safety Monitoring

The principle investigator will monitor safety and laboratory data throughout the study and should discuss safety concerns with the sponsor immediately upon occurrence or awareness of the concern to determine whether the participant should continue or discontinue study drug.

8.2.5.1. Hepatic Safety Monitoring

If a study patient experiences elevated ALT $\geq 3X$ ULN, ALP $\geq 2X$ ULN, or elevated TBL $\geq 2X$ ULN, liver testing (Section 10.6) should be repeated within 3 to 5 days including ALT, AST, ALP, TBL, direct bilirubin, gamma-glutamyl transferase, and creatine kinase to confirm the abnormality and to determine if it is increasing or decreasing. If the abnormality persists or worsens, clinical and laboratory monitoring should be initiated by the investigator and in consultation with the study Lilly Medical. Monitoring of ALT, AST, TBL, and ALP should continue until levels normalize or return to approximate baseline levels.

Hepatic Safety Data Collection

Additional safety data should be collected via the eCRF if 1 or more of the following conditions occur:

- elevation of ALT to $\geq 5X$ ULN on 2 or more consecutive blood tests
- elevated TBL to $\geq 2X$ ULN (except for cases of known Gilbert's syndrome)
- elevation of ALP to $\geq 2X$ ULN on 2 or more consecutive blood tests
- patient discontinued from treatment due to a hepatic event or abnormality of liver tests
- hepatic event considered to be a SAE.

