5.2. Exclusion Criteria

Participants are excluded from the study if any of the following criteria apply:

Medical Conditions

- [10] Have a history of greater than 1 episode of ketoacidosis or hyperosmolar state/coma requiring hospitalization in the 6 months prior to screening.
- [11] Have had any episodes of severe hypoglycemia and/or hypoglycemia unawareness within the 6 months prior to screening.
- [12] Cardiovascular (CV): have had any of the follow CV conditions: acute myocardial infarction, New York Heart Association Class III or IV heart failure (Section 10.6), or cerebrovascular accident (stroke).
- [13] Gastrointestinal: have undergone gastric bypass (bariatric) surgery or restrictive bariatric surgery (e.g., Lap-Band®) prior to screening.
- [14] Hepatic: have acute or chronic hepatitis, or obvious clinical signs or symptoms of any other liver disease except non-alcoholic fatty liver disease (NAFLD) (i.e., patients with NAFLD are eligible for participation), and/or have elevated liver enzyme measurements, as determined by the central laboratory at screening and as indicated below:
- Total bilirubin >1.5x the upper limit of normal (ULN) in the absence of Gilbert's syndrome, or
 - Alanine aminotransferase (ALT)/serum glutamic pyruvic transaminase (SGPT) >2.0x ULN, or
 - Aspartate aminotransferase (AST)/serum glutamic oxaloacetic transaminase (SGOT) >2.0x ULN
- [15] Renal: have an estimated glomerular filtration rate (eGFR) <30 mL/min/1.73 m², calculated by the Chronic Kidney Disease-Epidemiology equation, as determined by the central laboratory at screening.

- [16] Have fasting triglycerides >400 mg/dL or non-fasting >600 mg/dL.
- [17] Have experienced significant weight loss or gain (>5%) in body weight in the 3 months prior to screening (Visit 1).
- [18] Have active or untreated malignancy, or have been in remission from clinically significant malignancy (other than basal cell or squamous cell skin cancer) for less than 5 years or are at increased risk for developing cancer or a recurrence of cancer in the opinion of the investigator.
- [19] Have known hypersensitivity or allergy to any of the study medications or their excipients.

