7.1.1. Permanent Discontinuation from Study Treatment

Possible reasons leading to permanent discontinuation of investigational product include, but are not limited to:

- **Participant decision**
 - the patient or the patient's designee, for example, parents or legal guardian requests to discontinue IP.
- **Hepatic event or liver test abnormality:** Participants who are discontinued from IP due to a hepatic event or liver test abnormality should have additional hepatic safety data collected via eCRF

Discontinuation of the IP for abnormal liver tests **should be** considered by the investigator when a participant meets one of the following conditions after consultation with the sponsor-designated medical monitor:

- ALT or AST >8X ULN
- ALT or AST >5X ULN for more than 2 weeks
- ALT or AST >3X ULN and total bilirubin level (TBL) >2X ULN or international normalized ratio (INR) >1.5
- ALT or AST >3X ULN with the appearance of fatigue, nausea, vomiting, right upper-quadrant pain or tenderness, fever, rash, and/or eosinophilia (>5%)
- alkaline phosphatase (ALP) >3X ULN
- ALP >2.5X ULN and TBL >2X ULN
- ALP >2.5X ULN with the appearance of fatigue, nausea, vomiting, right quadrant pain or tenderness, fever, rash, and/or eosinophilia (>5%)

In addition, participants will be discontinued from the IP in the following circumstances:

- if a patient is inadvertently enrolled and it is determined that continued treatment with IP would not be medically appropriate (see Section 7.2.1)

- if a patient is diagnosed with an active or untreated malignancy (other than basal or squamous cell skin cancer, in situ carcinomas of the cervix, or in situ prostate cancer) after randomization
- if the investigator or sponsor decides that the patient should be withdrawn from IP; if the investigator decides to permanently discontinue IP because of an SAE or a clinically significant laboratory value, Lilly or its designee should be alerted immediately
- if the investigator, after consultation with Lilly Medical, determines that a systemic hypersensitivity reaction has occurred related to study drug administration, the participant should be permanently discontinued from IP.

See the Schedule of Activities for data to be collected at the time of intervention discontinuation and follow-up and for any further evaluations that need to be completed.

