8.2. Safety Assessments

Planned time points for all safety assessments are provided in the Schedule of Activities, Section 1.3.

The following safety assessments will be evaluated as secondary objectives:

- Incidence and rate of hypoglycemia
- Incidence of treatment-emergent SAEs
- Clinical laboratory assessments with specific focus on liver aminotransferase changes.

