8.2.6. Clinical Safety Laboratory Assessments

See Section 10.2 for the list of clinical laboratory tests to be performed and the Schedule of Activities (Section 1.3) for the timing and frequency.

The investigator must review the laboratory report, document this review, and record any clinically relevant changes occurring during the study in the AE section of the eCRF. The laboratory reports must be filed with the source documents. Clinically significant abnormal laboratory findings are those which are not associated with the underlying disease, unless judged by the investigator to be more severe than expected for the participant's condition.

All laboratory tests with values considered clinically significantly abnormal during participation in the study or within 6 weeks after the last dose of study intervention (that is, within the follow-up period) should be repeated until the values return to normal or baseline or are no longer considered clinically significant by the investigator or Lilly medical.

- If such values do not return to normal/baseline within a period of time judged reasonable by the investigator, the etiology should be identified and the sponsor notified.
- All protocol-required laboratory assessments, as defined in Section 10.2, must be conducted in accordance with the laboratory manual and the Schedule of Activities.

- If laboratory values from non-protocol specified laboratory assessments performed at the institution's local laboratory require a change in participant management or are considered clinically significant by the investigator (e.g., SAE or AE or dose modification), then the results must be recorded in the eCRF.

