10.5. Appendix 5: Liver Safety: Suggested Actions and Follow-up Assessments

Hepatic Monitoring Tests

Hepatic Hematology^a

Hemoglobin
 Hematocrit
 RBC
 WBC
 Neutrophils, segmented
 Lymphocytes
 Monocytes
 Eosinophils
 Basophils
 Platelets

Hepatic Chemistry^a

Total bilirubin
 Direct bilirubin
 Alkaline phosphatase
 ALT
 AST
 GGT
 CPK

Haptoglobin^a

Hepatic Coagulation^a

Prothrombin Time
 Prothrombin Time, INR

Hepatic Serologies^{a,b}

Hepatitis A antibody, total
 Hepatitis A antibody, IgM
 Hepatitis B surface antigen
 Hepatitis B surface antibody
 Hepatitis B Core antibody
 Hepatitis C antibody
 Hepatitis E antibody, IgG
 Hepatitis E antibody, IgM

Anti-nuclear antibody^a

Alkaline Phosphatase Isoenzymes^a

Anti-smooth muscle antibody (or anti-actin antibody)^a

Abbreviations: ALT = alanine aminotransferase; AST = aspartate aminotransferase; CPK = creatinine phosphokinase; GGT = gamma-glutamyl transferase; Ig = immunoglobulin; INR = international normalised ratio; RBC = red blood cells; WBC = white blood cells.

^a Assayed by Sponsor-designated or local laboratory.

^b Reflex/confirmation dependent on regulatory requirements and/or testing availability.

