10.6. Appendix 6: New York Heart Association Cardiac Disease Classification

Functional Capacity

Class I

Study participants with cardiac disease but without resulting limitation of physical activity. Ordinary physical activity does not cause undue fatigue, palpitation, dyspnea, or anginal pain.

Class II

Study participants with cardiac disease resulting in slight limitation of physical activity. They are comfortable at rest. Ordinary physical activity results in fatigue, palpitation, dyspnea, or anginal pain.

Class III

Study participants with cardiac disease resulting in marked limitation of physical activity. They are comfortable at rest. Less than ordinary activity causes fatigue, palpitation, dyspnea, or anginal pain.

Class IV

Study participants with cardiac disease resulting in inability to carry on any physical activity without discomfort. Symptoms of heart failure or the anginal syndrome may be present even at rest. If any physical activity is undertaken, discomfort increases

1994 Revisions to Classification of Functional Capacity and Objective Assessment of Patients with Diseases of the Heart

Reprinted with permission

www.americanheart.org

© 2011, American Heart Association, Inc.

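### The hepatic retest rule in Protocol 8.2.5.1 leaves AST out of its trigger, does not name INR, and cites the NYHA appendix (10.6) instead of the liver appendix (10.5)

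*Protocol*

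**What the plan says.** Protocol 8.2.5.1 (Hepatic Safety Monitoring) sets three retest triggers: ALT at or above 3X ULN, ALP at or above 2X ULN, and total bilirubin (TBL) at or above 2X ULN. When one is met, "liver testing (Section 10.6) should be repeated within 3 to 5 days including ALT, AST, ALP, TBL, direct bilirubin, gamma-glutamyl transferase, and creatine kinase". If the abnormality persists or worsens, further monitoring follows in consultation with the sponsor's medical staff, and ALT, AST, TBL and ALP are tracked until they settle.

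Protocol 7.1.1 lists seven liver-test conditions under which the investigator should consider stopping study drug after consulting the medical monitor. Two matter most here: "ALT or AST >5X ULN for more than 2 weeks" and "ALT or AST >3X ULN and total bilirubin level (TBL) >2X ULN or international normalized ratio (INR) >1.5".

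Section 10.6, cited in the retest sentence, is headed "New York Heart Association Cardiac Disease Classification". The hepatic test list is in Section 10.5, where "Prothrombin Time, INR" appears under coagulation.

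Protocol 8.2.6 has a general repeat rule covering "All laboratory tests with values considered clinically significantly abnormal during participation in the study", with no numerical threshold and no interval. Among the safety assessments evaluated as secondary objectives, Protocol 8.2 lists "Clinical laboratory assessments with specific focus on liver aminotransferase changes".

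**The concern.** The rule that secures prompt confirmation does not match the rule that uses the confirmed result. Section 7.1.1 treats ALT and AST as interchangeable, and so does exclusion criterion 14, which has its own AST limit ("Aspartate aminotransferase (AST)/serum glutamic oxaloacetic transaminase (SGOT) >2.0x ULN"). The SAP's elevation tables (5.10.5.2) are also built for both enzymes. Only the retest trigger drops AST, and the protocol gives no reason.

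The INR gap and the wrong section number compound each other. A correct reference to 10.5 would have brought PT/INR into the retest. As written, a site that follows the reference reaches a heart-failure scale, and the INR half of a discontinuation criterion has no instructed source of data.

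What is at stake is the speed and consistency with which sites confirm a possible liver signal. Estimates of efficacy, power and error rates are not affected.

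**Working it through.** The plan states no figure to reproduce. The check compares the sections and then works out the waiting time from the visit schedule.

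**Where each test appears**

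| Place | ALT | AST | INR |
|---|---|---|---|
| Exclusion criterion 14 (5.2) | yes | yes | no |
| Retest trigger (8.2.5.1) | yes | **no** | no |
| Named repeat panel (8.2.5.1) | yes | yes | **no** |
| Discontinuation criteria (7.1.1), of 7 | 4 | 4 | 1 |
| Routine laboratory list (10.2) | yes | yes | **no** |
| Hepatic panel (10.5) | yes | yes | yes |
| Extra hepatic eCRF data, 5X on consecutive tests (8.2.5.1) | yes | **no** | no |
| Elevation tables at 3X, 5X, 10X (SAP 5.10.5.2) | yes | yes | no |
| Patient listing, 5X on consecutive tests (SAP 5.10.5.2) | yes | **no** | no |

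**Which criteria need more than one routine panel.** Of the four criteria naming AST, three (above 8X; above 3X with bilirubin or INR; above 3X with symptoms or eosinophilia) can be judged from one blood draw plus clinical findings, apart from the INR alternative. The fourth, above 5X for more than two weeks, needs a second AST value. For ALT, 8.2.5.1 secures an early repeat and continued monitoring if the rise persists. For an isolated AST rise it does neither.

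**Section references.** Exclusion criterion 12 cites 10.6 correctly for NYHA class, so the appendix numbering is right and the citation in 8.2.5.1 is wrong. No other body text sends a site to 10.5.

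**Wait for the next scheduled chemistry panel.** In the Schedule of Activities (Protocol 1.3), allowing for row labels shifted in the extracted table, chemistry falls at Weeks 0, 3, 6, 12, 16, 24 and 26 from randomization to end of treatment. Visit 3 (Week 0) has no window and the other six visits have ±3 days. Nominal gap = 7 × difference in weeks. The range subtracts and adds the windows at both ends.

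| Interval (weeks) | Nominal gap (days) | Range with windows (days) |
|---|---|---|
| 0 to 3 | 7 × 3 = 21 | 18 to 24 |
| 3 to 6 | 7 × 3 = 21 | 15 to 27 |
| 6 to 12 | 7 × 6 = 42 | 36 to 48 |
| 12 to 16 | 7 × 4 = 28 | 22 to 34 |
| 16 to 24 | 7 × 8 = 56 | 56 − 6 = 50 to 56 + 6 = 62 |
| 24 to 26 | 7 × 2 = 14 | 8 to 20 |

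Five of the six nominal gaps exceed 14 days, and those five stay above 14 days at the short end of their windows. The comparison for ALT is 3 to 5 days.

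**The case against.** The other side has several fair points.

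- **ALT-led monitoring fits the stated hazard.** The synopsis justifies the 26-week duration by an ALT increase seen with an earlier basal insulin, and the protocol and SAP use the same ALT-only item at 5X ULN. This supports reading that item as deliberate, and it is the weakest part of the concern. It does not explain why AST counts for discontinuation but not for the repeat that informs it.
- **The uncovered case is narrow.** A rise in ALT, ALP or bilirubin to its trigger already prompts a panel that includes AST, so AST with bilirubin at 2X or more is covered. What remains is isolated AST elevation, plus either enzyme with raised INR and bilirubin below 2X.
- **Discretion fills part of the gap.** Section 8.2.6 asks for repeats of values judged clinically significant. Section 8.2.5 has the investigator review laboratory data throughout, the repeat panel is not worded as exhaustive, Section 10.2 permits extra tests, and 7.1.1 names INR and requires consultation. All of this allows the right action, but none of it instructs a timed AST repeat or an INR.
- **AST cases stay visible.** SAP 5.10.5.2 tabulates AST at 3X, 5X and 10X using maximum values, and Protocol 9.4.6.4 lists out-of-range results. The reporting gap is therefore confined to the extra hepatic eCRF data, the special patient listing and its time-course plots.
- **Endpoint status is mixed.** Section 8.2 puts aminotransferase changes with the secondary safety assessments, while the objectives table (Protocol 3) and SAP 4.3 class them as exploratory. This lowers the analytic weight but has no bearing on patient monitoring.

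**Conclusion.** The concern holds in all three parts: AST is missing from the trigger, INR is not named in the repeat panel, and the section reference is wrong. The wrong reference sits in operative safety instructions and separates the INR alternative in 7.1.1 from the only place where the test is listed.

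The consequence is slower or site-dependent confirmation of an isolated AST rise or a raised INR. Because the 7.1.1 conditions prompt consideration after consultation, no automatic stop is missed. The 50-to-62-day figure is the longest wait on treatment. It assumes that no repeat is ordered under 8.2.6 and that the chemistry row has been read correctly from the extracted table. The documents give no basis for estimating how many participants would be affected. Sample size, power, alpha and the primary analysis are unchanged. The correction should be made.

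**What to change.** In Protocol 8.2.5.1:

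1. Change the first trigger to ALT or AST at or above 3X ULN.
2. Add PT/INR to the named repeat panel.
3. Replace the reference to Section 10.6 with Section 10.5.

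For consistency, and as a lower priority, extend the item on 5X ULN on consecutive tests to ALT or AST, both in 8.2.5.1 and in the patient listing in SAP 5.10.5.2. The thresholds in 7.1.1 stay as they are.

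The cost is wording in one protocol section and one SAP list item, plus a few additional repeat panels and INR tests. The lower-priority change also widens a hepatic eCRF data-collection trigger, so it is slightly more than an editorial correction. The protocol edits would go through IRB/IEC approval as an amendment under Section 10.1.1.

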8.2.6. Clinical Safety Laboratory Assessments

See Section 10.2 for the list of clinical laboratory tests to be performed and the Schedule of Activities (Section 1.3) for the timing and frequency.

The investigator must review the laboratory report, document this review, and record any clinically relevant changes occurring during the study in the AE section of the eCRF. The laboratory reports must be filed with the source documents. Clinically significant abnormal laboratory findings are those which are not associated with the underlying disease, unless judged by the investigator to be more severe than expected for the participant's condition.

All laboratory tests with values considered clinically significantly abnormal during participation in the study or within 6 weeks after the last dose of study intervention (that is, within the follow-up period) should be repeated until the values return to normal or baseline or are no longer considered clinically significant by the investigator or Lilly medical.

- If such values do not return to normal/baseline within a period of time judged reasonable by the investigator, the etiology should be identified and the sponsor notified.
- All protocol-required laboratory assessments, as defined in Section 10.2, must be conducted in accordance with the laboratory manual and the Schedule of Activities.

- If laboratory values from non-protocol specified laboratory assessments performed at the institution's local laboratory require a change in participant management or are considered clinically significant by the investigator (e.g., SAE or AE or dose modification), then the results must be recorded in the eCRF.

8.2.7. Body Weight

Body weight will be measured at prespecified time points (see Schedule of Activities, Section 1.3). Patients will be weighed in a light hospital gown or standard clinical research site scrubs at approximately the same time in the morning after an overnight fast and after evacuation of bowel and bladder contents, if possible.

Weight will be measured once at screening (non-fasting) and recorded in the source document and eCRF. At lead-in and randomization (Visit 2 and Visit 3, respectively) and all subsequent visits indicated in the Schedule of Activities (Section 1.3), weight will be measured twice, with the patient stepping off the scale between measurements.

Both weight measurements will be recorded in the source document and the eCRF. Calibrated (within 6 months prior to study start) scales should be used. The same scale should be used for all weight measurements throughout the study and should not be moved during the conduct of the study.

8.3. Adverse Events and Serious Adverse Events

AEs will be reported by the participant (or, when appropriate, by a caregiver, surrogate, or the participant's legally authorized representative).

The investigator and any qualified designees are responsible for detecting, documenting, and recording events that meet the definition of an AE or SAE and remain responsible for following up AEs that are serious, are considered related to the study intervention or study procedures, or that caused the participant to discontinue the study intervention or the study (see Section 7).

8.3.1. Time Period and Frequency for Collecting AE and SAE Information

All AEs occurring after signing the ICF are recorded in the eCRF and assessed for serious criteria.

The SAE reporting to sponsor begins after the patient has signed the ICF and has received study drug. However, if an SAE occurs after signing the ICF, but prior to receiving LY3209590, it needs to be reported ONLY if it is considered reasonably possibly related to study procedures.

All SAEs will be recorded and reported to the sponsor or designee immediately and under no circumstance should this exceed 24 hours, as indicated in Section 10.3. The investigator will submit any updated SAE data to the sponsor within 24 hours of it being available.

Investigators are not obligated to actively seek AE or SAE after conclusion of the study participation. However, if the investigator learns of any SAE, including a death, at any time after a participant has been discharged from the study, and he/she considers the event to be reasonably related to the study intervention or study participation, the investigator must promptly notify the sponsor.

8.3.2. Method of Detecting AEs and SAEs

The method of recording, evaluating, and assessing causality of AE and SAE and the procedures for completing and transmitting SAE reports are provided in Section 10.3.

Care will be taken not to introduce bias when detecting AEs and/or SAEs. Open-ended and non-leading verbal questioning of the participant is the preferred method to inquire about AE occurrences.

8.3.3. Follow-up of AEs and SAEs

After the initial AE/SAE report, the investigator is required to proactively follow each participant at subsequent visits/contacts. All SAEs, and AEs of special interest (AESIs) (as defined in Section 8.3.7), will be followed until resolution, stabilization, the event is otherwise explained, or the participant is lost to follow-up (as defined in Section 7.3). Further information on follow-up procedures is provided in Section 10.3.

